AM02	3.0	5 th July 2017	[name] and [name]	by an independent statistician. 10.3: Updates to analysis plan. 11: New health economic section. 14.5: Addition of NHS number to the eCRF. 17: Additional references (health economics). 18: Original questionnaire as a research tool. 19: 5Q-5D-5L telephone questionnaire. 20: Proxy 5Q-5D-5L questionnaire for patients lacking capacity. Other minor administrative updates throughout. - Addition of Co-Investigator/Trial Statistician 1. Updated study end date 7.1 Provision for up to six further centres 8. Clarity of IPH definition for binary analysis
AM03	4.0	16 th January 2018	[name]	 Addition of additional principal investigators Addition of another funder Change of contact details for chief investigator

1. SYNOPSIS

Study Title	Pilot Study for a randomised trial comparing the influence of forced air versus resistive fabric warming technologies on post-operative infection rates following orthopaedic implant surgery in adults.	
Short title	Reducing Implant Infection in Orthopaedics (RIIiO) Pilot Study	
Acronym	RIIiO Pilot Study	
Trial Design	Parallel group, open label 1:1 randomised pilot study comparing post- operative infection rates following orthopaedic implant surgery using direct contact Resistive Fabric Warming (RFW) or Forced Air Warming (FAW)	
Trial Participants	Adults of 60 years or over undergoing hemiarthroplasty following hip fracture	
Planned Sample Size	There is no upper limit for the sample size. Progression rules for the definitive trial will include a projection of 100 participants per year at each pilot site. Participants will be recruited over a minimum period of 12 months at each site.	
Follow-Up Duration	90 days from the date of surgery	
Planned Trial Period	14 th November 2016 to 31 st December 2018	
Primary Objective	The primary objective of the pilot study is to inform data management and recruitment strategies for a definitive trial comparing infection rates following orthopaedic surgery with two warming technologies. The primary objective of the full trial: "Is there a significant difference in the incidence of post-operative infection after hemiarthroplasty using Forced Air Warming (FAW) as compared to Resistive Fabric Warming (RFW)?"	
Secondary Objectives	The secondary objective of the pilot study is to explore the feasibility of collecting resource use and quality of life data, to inform the design of the health economics component of the proposed fully powered trial.	
	The secondary objective of the full trial: "Is there a significant cost- effectiveness advantage to the NHS of using either direct contact resistive fabric warming (RFW) or forced air warming (FAW)?"	
Primary Endpoints	Numbers recruited and observed event rate for definitive deep surgical site infection (SSI) within 90 days of surgery.	
Secondary Endpoints	Superficial SSI, inadvertent perioperative hypothermia (IPH), length of hospital stay, patient reported outcome measures for quality of life score (EQ-5D-5L), resource utilisation and serious adverse events (SAEs) including death.	
Investigational Medicinal Products		
	None	

2. ABBREVIATIONS

Z. ADDRE	VIATIONS
BSUH	Brighton and Sussex University Hospitals NHS Trust
CDC	Centers for Disease Control
CI	Chief Investigator
CRF	Case Report Form
CTU	Clinical Trials Unit
DSMB	Data and Safety Monitoring Board
FAW	Forced Air Warming
GCP	Good Clinical Practice
GP	General Practitioner
HRA	Health Research Authority
ICF	Informed Consent Form
ICH	International Conference on Harmonisation
ICMJE	International Committee of Medical Journal Editors
IPH	Inadvertent Perioperative Hypothermia
ІТТ	Intention to Treat
NHS	National Health Service
NICE	National Institute for Health and Care Excellence
NIHR	National Institute for Health Research
NITCAR	National Infection Trainee Collaborative for Audit and Research
PI	Principal Investigator
PHE	Public Health England
PIS	Participant/ Patient Information Sheet
RAFT	Research and Audit Federation for Trainees network in anaesthetics
R&D	NHS Trust R&D Department
REC	Research Ethics Committee
RFW	Resistive Fabric Warming
SAE	Serious Adverse Event
SAP	Statistical Analysis Plan
SOP	Standard Operating Procedure
SSI	Surgical Site Infection
TARN	Trauma Audit and Research Network
TSC	Trial Steering Committee
UCV	Laminar flow Ultra Clean Ventilation

UKCIRG	United Kingdom Clinical Infection Research Group	
WHITE	World Hip Trauma Evaluation	

3. BACKGROUND AND RATIONALE

Around 250,000 lower limb orthopaedic implants are performed in the UK each year, including 160,000 knee or hip arthroplasties and 70,000 hip fracture repairs or hemiarthroplasties. These are amongst the most cost effective interventions for any medical condition treated under the NHS. However, postoperative infection complicates 1-3% of joint implants in general and between 2.3% (passive surveillance) and 7.3% (active surveillance) of hip fracture repairs in particular (Dale et al 2011, Ridgeway et al 2005). Around half of these are classified as deep infections which almost always require repeat surgery, a prolonged course of antibiotics and extensive rehabilitation. Furthermore, patients with implant associated infections have a significantly worse long term outcome and mortality as compared to patients following uncomplicated implant surgery. The consequences of surgical site infection (SSI) in this group of patients are therefore considerable. Despite the limited risk of SSI for an individual, orthopaedics and trauma surgery was identified as the most common source of SSI in inpatients during a point prevalence survey in England in 2011 (Health Protection Agency 2011). Given that arthroplasty rate more than doubled between 2000 – 2009 in the USA and Denmark (Lamagni T 2014), it seems inevitable that, in the absence of new initiatives, implant related SSI will be an increasingly important burden to patients and to the health economy. Assessing available interventions aimed at limiting the incidence of SSI is therefore an urgent priority.

In response to the global threat of emerging antimicrobial resistance, health care services are under increasing pressure to reduce antibiotic consumption. The most effective way to achieve this is to reduce infection rates. This is particularly true of bone and joint infections which commonly require a course of antibiotic therapy lasting up to six months (Osmon et al 2013). Reducing overall exposure to antibiotics will reduce the threat of emerging resistance and is likely to limit the risks of health care associated infections such as *Clostridium difficile*, methicillin resistant *Staphylococcus aureus* (MRSA) and carbapenemase producing Enterobacteriaceae (CPE). The considerable concern over the potential threat that emerging antibiotic resistance poses to the safety and efficacy of surgical procedures will sustain the search for widely generalizable mechanisms to limit the risk of infection and improve patient outcomes.

There are a number of ways in which the risk of surgical site infection may be reduced. In orthopaedic surgery, use of laminar flow ultra clean ventilation (UCV) became standard practice in the UK following a large randomised trial of 8055 patients (Lidwell et al 1982) in which post-operative infection rate was halved. However, because UCV depends upon high volume and high velocity filtered air, it exacerbates loss of body heat during surgery so that patients are rendered at risk of inadvertent perioperative hypothermia (IPH). As well as being associated with greater blood loss, delayed anaesthetic recovery and an excess length of hospital stay, IPH also predisposes the patient to post-operative infection. This was initially demonstrated in an individually randomised trial involving 200 patients undergoing colorectal surgery, and confirmed in 'clean' surgery (hernia repair, varicose vein surgery and breast surgery) in a randomised trial involving 420 patients; both trials showed a relative reduction in the incidence of surgical site infection of well over 50% for patients maintained at or above a temperature of 36°C (Kurz et al 1996; Melling et al 2001). These findings have been extrapolated such that perioperative patient warming is now recommended for any operation lasting >30 minutes. NICE has produced guidelines specifically relating to the prevention of IPH during surgery and has specified the need for research on mechanisms and devices to achieve this (NICE Clinical Guideline April 2008).

In current clinical practice, there are two principal technologies for keeping patients warm during surgery: (1) Forced Air Warming (FAW) and (2) direct contact Resistive Fabric Warming (RFW).

FAW relies upon electrically heated air being delivered through a disposable hollow duvet which is placed over the patient. Warmed air then exits through holes over the patient's skin and warms the patient by convection. FAW is the most widely used active warming technology in the UK. It is incorporated into national recommendations for the prevention and management of inadvertent perioperative hypothermia, supported by evidence for both its clinical effectiveness and cost effectiveness (NICE Clinical Guideline April 2008).

RFW is similar in principle to an electric blanket. It uses low voltage DC current passing through semiconductive polymer fibre fabric which warms the patient by conduction. In 2011 NICE issued technology guidance relating to a specific RFW product (NICE medical technology guidance 7 August 2011). NICE found sufficient evidence to suggest that its effectiveness was similar to that of FAW in maintaining core temperature during surgery. There was no statement as to its clinical effectiveness in reducing the risk of SSI.

There is limited evidence to guide the choice of active warming technologies. Theoretical studies looking at air movement and particulates in sham orthopaedic surgery have suggested that FAW may result in interference with ultraclean ventilation systems commonly used in orthopaedic surgery (McGovern et al 2011; Legg et al 2012) but this has not been proven to influence clinical outcome. Two relevant clinical studies have investigated perioperative warming specifically in relation to orthopaedic post-operative infection rates. The first was a non-randomised study involving 30 patients; no events were observed within the first six post-operative months in either the FAW group (20 patients) or the group which had no active intraoperative warming (10 patients) (Moretti et al 2009). The second study compared infection rates before and after a change from FAW to RFW in a single NHS Trust. The study collected data relating to 1,437 consecutive elective hip or knee replacements over a three-year period. The results suggested a significant reduction in deep post-operative infections rates (from 3.1% to 0.8% p=0.02) when FAW was replaced by RFW (McGovern et al., 2011). However, the outcome data are subject to potential confounding by other factors which may have changed during the study period. The findings, therefore, do not constitute sufficiently robust evidence upon which to base a change in practice.

Summary Justification for a Pilot Study and Progression Plan

We postulate that the risk of post-operative orthopaedic implant infection may be influenced by the choice of intraoperative warming technology. We plan to investigate this through a multi-centre superiority trial comparing FAW and RFW in adults undergoing hemiarthroplasty following hip fracture. Health economic evaluation will form the secondary aim of the study.

The biggest barrier to a successful funding application for this trial is the number of participants required. Hemiarthroplasty carries a risk of deep SSI of around 2.5%. To provide 90% power to demonstrate an absolute risk reduction of 1%, using a 5% significance level, a trial will need to recruit approximately 8630 participants over a 3-year period. To ensure a robust application, we will conduct a pilot study across a limited number of NHS sites to demonstrate that the recruitment strategy, randomisation process and follow-up assessments are appropriate and effective. Provided that no major strategic changes are required, we anticipate that refinements can be adopted and the study rolled out to additional centres without a prolonged break in recruitment at pilot centres. Pilot data will subsequently be transferred to the full trial and will contribute to the final analysis.

The United Kingdom Clinical Infection Research Group (UKCIRG) is a research collaboration consisting of 43 NHS trusts in the UK. Its current interventional trials include The OVIVA Study (Oral vs. Intravenous Antibiotics in bone and joint infection) which recruits at 27 centres, and the ARREST Trial (Adjunctive Rifampicin to Reduce Early mortality in Staph aureus bacteraemia) which recruits at 30 centres. The WHITE cohort is a collaboration of 16 NHS trusts recruiting patients under a single comprehensive treatment pathway, based upon the NICE Hip Fracture Guidelines, and provides core outcome measurements collected within the framework of the UK National Hip Fracture Database. Assuming that 30 of the centres from these networks are willing to participate, progression from pilot to a definitive trial will be considered if recruitment at each pilot centre exceeds an average of 2 participants per week or projects to over 100 per year after six months of activity. A second progression target designed to assess data management strategy will be defined by follow-up data for primary endpoints at Day 30 being available for >90% of participants six months after the start of the pilot study.

4. **OBJECTIVES AND OUTCOME MEASURES**

[figure not shown]
- **Primary Objective** The primary objective of the RIIiO pilot study is to inform and assess the recruitment and data management strategies for a full trial.
- **Secondary Objectives** The secondary objective of the pilot study is to confirm the methodology for health economic evaluation in the context of the full trial.

Follow-Up Time Points	Participants will be followed up at 30 days and 90 days following surgery.	
Primary Outcome Measure	Recruitment rate and data completion (pilot study) and definitive deep surgical site infection (SSI) within 90 days of surgery (main trial).	
Secondary Outcome Measures	come Measures Superficial SSI, documented IPH, length of hospital stay, patient reported	
	outcome measures for quality of life score (EQ-5D-5L), resource utilisation and serious adverse events (SAEs) including death.	

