At the earliest appropriate opportunity after recovery from surgery, a member of the research team will approach randomised participants to provide them with study information and to seek written personal consent to continue in the study. They will be given as much time as they wish to discuss the study, to ask questions and talk to their family and carers. For those who have persisting lack of capacity, written agreement from a personal consultee will be sought. Participants (or their representatives) who do not wish to be contacted or who do not wish to complete questionnaires will be asked for consent to allow the research team to access and use routinely captured NHS data; these may include data recorded by their GP, the National Hip Fracture database and the Surgical Site Surveillance database. Alternatively, the participant (or their representative) can decline participation completely. The Information Sheet, consent form and consultee declaration state clearly that participants or consultees can withdraw their consent or advice at any time without giving a reason.

Signed consent forms will be stored in the investigator site file. A copy will be given to the participant (or their representative) and a copy will be placed in the participant's medical notes.

On occasion, patients may be able to provide consent before their operation, for example those whose surgery is delayed for clinical reasons. These patients will be approached prior to surgery for consent to participate in the study. If, despite delayed surgery, a patient lacks capacity the research team will approach a consultee.

Best efforts will be made to involve participants who, temporarily or permanently, lack capacity to make an informed decision. The research team will make a judgement as to the amount and complexity of the information that the patient is able to understand and retain on an individual basis. Appropriate information will be communicated to the participant and updated as their understanding changes. At all times the study team will act in accordance with the participant's best interests.

Any new information that arises during the study that may affect participants' willingness to take part will be reviewed by the TSC; if necessary this will be communicated to all participants and a revised consent form prepared.

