7.4. Randomisation and limitation of bias

Prior to surgery, participants will be randomised 1:1 in randomly permuted blocks through an established software package to either Forced Air Warming or direct contact Resistive Fabric Warming. No stratification factors will be employed. In case of software failure, randomisation envelopes will be prepared in advance under the supervision of a qualified statistician and held by the local study team for immediate use in the emergency setting.

This will be an open label trial. Although participants will not be directly informed of their randomised allocation, they may become aware of this either immediately before or upon recovery from anaesthesia. Similarly, it is not possible to blind the direct medical care team or the local study team as to which warming technology is utilised during surgery. Any consequent risk of bias will be limited by the use of a blinded end point committee for the assessment of relevant potential endpoints. For all potential deep SSIs, the end point committee will be provided with a summary of the participant's medical records relevant to the clinical episode, (including presentation, operative findings, laboratory results, radiology reports and treatment) redacted for personal identifiers and any information relating to their randomisation or intraoperative thermoregulation. At the time of randomisation, the participant's initials, NHS number and a computer-generated study number will be recorded on an enrolment log. Justification for use of NHS numbers comes from previous multicentre studies in which the randomisation software requires all

participants to have a primary identifier of the same alphanumeric structure and with no opportunity for duplicates.

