10.3. Analysis of Outcome Measures for the full trial

Pending recommendations arising from the pilot study, we assume that the analysis of outcome measures for the full trial will take the following form:

Analysis of the primary endpoint:

Based on the ITT population (i.e. participants analysed according to their allocated trial arm, regardless of their compliance with the protocol), the proportions of participants in either treatment arm experiencing a definitive deep surgical site infection within 90 days from surgery will be calculated.

We will determine the superiority of either of the two trial interventions by assessing if there is a statistically significant difference in the log-odds of infection between the randomised treatment arms using a logistic regression model with randomised treatment as a fixed effect; superiority of either intervention is defined by the treatment coefficient being statistically significant at the 5% level. Covariates considered *a priori* to be prognostic of outcome may be included to give an adjusted odds ratio. These would be agreed by consensus and written into the full statistical analysis plan and signed off prior to analysis of unblinded data.

Secondary analyses will include a per protocol analysis based on all participants who have received their randomised intervention. A survival analysis will be performed to assess potential differences in the time to diagnosis of definitive deep surgical site infections. Health economic evaluation will be conducted by a dedicated health economist based on capital, maintenance and treatment costs, as well as EQ-5D-5L data, and will include the costs of complications.

Other secondary endpoint analyses will include regression models to calculate estimates of treatment differences for the primary and secondary outcomes unadjusted (primary analysis) and adjusted for age and co-morbidities (secondary analyses). These secondary analyses will focus on the consistency of point estimates and 95% confidence intervals rather than formal statistical significance testing.

Pre-defined subgroup analyses will use interaction tests to explore the consistency of treatment effects by trial site.

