Patients who are randomised but, for whatever reason, do not proceed to surgical management will be excluded from all analyses. For patients who withdraw their consent, no further data will be collected from follow-up questionnaires, but data collected up to the point of withdrawal and routine data from medical records will be included unless the participant denies access to their medical records.

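### The 8630 recruitment target is an evaluable number with no allowance for loss, and the per-centre progression threshold built on it has only about 4% headroom

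*Protocol*

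**What the plan says.** The sizing and the progression rules are in Section 3, Summary Justification for a Pilot Study and Progression Plan. With a deep SSI risk of about 2.5%, an absolute reduction of 1%, 90% power and a 5% significance level, "a trial will need to recruit approximately 8630 participants over a 3-year period". Thirty centres are assumed. Moving on to the full trial is contemplated where accrual at every pilot site "exceeds an average of 2 participants per week or projects to over 100 per year after six months of activity". The other rule asks that Day 30 primary endpoint data be available for more than 90% of participants six months after the pilot starts. Pilot data are to be carried into the full trial's final analysis.

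Other sections remove randomised participants from the analysis or allow them to leave it. Section 10.3 states that patients who "do not proceed to surgical management will be excluded from all analyses", and the withdrawal text after Section 7.6 has the site investigator withdraw them. Section 7.3 obtains consultee agreement before surgery in most urgent cases and seeks the participant's own consent afterwards. It adds: "Alternatively, the participant (or their representative) can decline participation completely". Section 10.3 also allows a withdrawing participant to deny access to medical records. The full trial's primary endpoint (Section 4, outcome table) runs to 90 days, not 30.

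**The concern.** A sample size formula gives the number of participants with a known outcome. Section 3 uses that number as the number to recruit and then sets the per-centre threshold close to it. If some randomised participants cannot be analysed, recruiting 8630 does not give 90% power. A centre rate that only just reaches 8630 has the same defect.

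This matters because the pilot's primary objective is to inform recruitment and data management for the full trial, and Section 3 names the number of participants as the main obstacle to funding. The threshold is the figure by which feasibility will be judged. The completeness rule is also read at Day 30, so passing it says little about how many participants will have a known 90-day status.

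**Working it through.** **Inputs.** From Section 3: p1 = 0.025, p2 = 0.015 (difference d = 0.01), power 90%, significance level 5%, total 8630, 3 years, 30 centres, threshold 100 per centre per year. From Section 7.4: "participants will be randomised 1:1 in randomly permuted blocks". Section 3 does not say whether the test is one- or two-sided. Two-sided is inferred from Section 10.3, where "superiority of either intervention is defined by the treatment coefficient being statistically significant at the 5% level".

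**1. Reproducing 8630.** With mean proportion 0.02, the uncorrected number per arm is

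n' = [1.960 x sqrt(2 x 0.02 x 0.98) + 1.2816 x sqrt(0.025 x 0.975 + 0.015 x 0.985)]^2 / 0.01^2 = (0.38805 + 0.25357)^2 / 0.0001 = 4116.8, so 4117 per arm and 8234 in total.

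The continuity correction gives

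n = (n'/4) x [1 + sqrt(1 + 4/(n' x d))]^2 = (4116.8/4) x (2.0475)^2 = 4314.5, so 4315 per arm and **8630** in total.

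The match is exact with zero loss. The other variants tried do not match: one-sided with correction 7106, unpooled 8228, arcsine 8110, log-odds 8416. The logistic model planned in Section 10.3 applies no continuity correction, so both 8630 and 8234 are carried below; the log-odds figure lies between them.

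**2. What loss does to 8630 recruited.**

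| Loss (assumed) | Evaluable | Power, corrected | Power, uncorrected |
|---|---|---|---|
| 0% | 8630 | 90.0% | 91.3% |
| 5% | 8198 | 88.4% | 89.9% |
| 10% | 7767 | 86.6% | 88.3% |

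**3. What the threshold delivers.** 100 x 30 x 3 = 9000, which is 370 (4.3%) above 8630. Starting from 9000, the loss that can be absorbed is 1 - 8630/9000 = 4.1%, or 1 - 8234/9000 = 8.5% against the uncorrected number. Both assume that all 30 centres recruit for the full three years.

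**4. Both rules met at their limits.** 9000 x 0.90 = 8100 evaluable, 4050 per arm.

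- Uncorrected: z = (0.01 x sqrt(4050) - 0.38805)/0.19786 = 1.255, power 89.5%.
- Corrected: inverting the correction, n' = n - 2/d + 1/(n x d^2) = 4050 - 200 + 2.5 = 3852.5; z = (0.01 x sqrt(3852.5) - 0.38805)/0.19786 = 1.176, power 88.0%.

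This takes Day 90 loss as equal to the tolerated Day 30 loss and counts no pilot participants.

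**5. Illustrations only.** The protocol gives no opening schedule, loss rate or carry-over number. Every scenario below is an assumption, at 100 per centre per year and 30 centres.

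| Opening | Loss | Pilot carry-over | Evaluable | Power, corrected / uncorrected |
|---|---|---|---|---|
| All at start | 10% | 300 | 8370 | 89.1% / 90.5% |
| All at start | 10% | 900 | 8910 | 90.9% / 92.1% |
| Linear over 6 months | 0% | 0 | 8250 | 88.6% / 90.1% |
| Linear over 12 months | 0% | 0 | 7500 | 85.3% / 87.1% |
| Linear over 12 months | 10% | 0 | 6750 | 81.3% / 83.5% |
| Linear over 12 months | 10% | 300 | 7020 | 82.8% / 84.9% |

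**6. Inflated targets, N/(1 - loss), and the rate they need.** The rate is the target divided by 30 x 3 = 90 centre-years, with no carry-over.

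| Loss | From 8630 | Rate per centre per year | From 8234 | Rate per centre per year |
|---|---|---|---|---|
| 5% | 9085 | 100.9 | 8668 | 96.3 |
| 10% | 9589 | 106.5 | 9149 | 101.7 |

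**The case against.** A reader might infer that the threshold leaves no margin and that the rule would approve an underpowered trial. The protocol does not support either reading.

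- **There is a margin.** 9000 exceeds 8630, and it absorbs 8.5% loss against the uncorrected number. On the other limb of the rule, 2 per week is 104 per year and 9360 in total. Less 10%, that is 8424, with 89.3% power corrected and 90.6% uncorrected.
- **Pilot data count.** Section 3 carries them into the final analysis. Three centres at 100 each would add 300, and nine centres 900 (Section 7.1 allows up to six more). The text does not say whether the three years include the pilot.
- **Ten per cent is not a planned loss rate.** It is a floor for Day 30 data in the pilot. Sections 7.3, 7.6 and 14.5 provide for GP, surveillance and other routine NHS data when contact fails or is refused, or when a participant has died. No rate is given for complete refusal or for surgery that does not take place.
- **The rule is not automatic.** Progression is only considered, the rates are minimums, and Sections 7.1 and 10.2 leave the number of sites to the pilot. Section 13 has the steering committee judge progression by extrapolation.

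All of this stands, and it limits the size of the point. Powers in the low or middle 80s need an assumed slow opening, usually with an assumed 10% loss. What remains is that 8630 is presented as a number to recruit although it contains no loss, and that the protocol does not bring carry-over, opening or loss into the calculation behind the threshold. Leaving site numbers to the pilot does not repair this, because the pilot will extrapolate towards the same uninflated target.

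**Conclusion.** The point holds, by a small margin. The protocol states an evaluable number as its recruitment target, while its own rules remove some randomised participants from the analysis. The progression threshold stands 4.3% above that number and presumes all 30 centres open throughout. If both progression rules are met only at their limits, power falls 2 points short of the stated 90% by the formula that reproduces 8630, and 0.5 points short without the correction. That result rests on a two-sided test, Day 90 loss equal to the tolerated Day 30 loss, no opening delay and no pilot carry-over.

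With low loss and quick opening, or with enough carry-over, 90% is reached. The protocol does not show that the trial would be materially underpowered. It shows that the target and threshold are not derived from the number of participants who can be analysed.

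**What to change.** 1. In Section 3, label 8630 as the evaluable number, state the formula and sidedness, and add a recruitment target with an explicit loss allowance. At 10% loss this is about 9590 with the continuity correction or about 9150 without it; at 5%, about 9085 or 8670. Say whether the correction is kept, since the planned logistic model does not use it.
2. Assess the data progression rule on evaluable participants: randomised, operated on, not fully declined, and with Day 90 status known.
3. Re-derive the per-centre rate from the new target, stating the centre-opening schedule and the pilot carry-over assumed. For 9590 with 30 centres open for three years and no carry-over, this is about 107 per year. Alternatively, keep 100 per year and state what it implies: 9589/300 = 32 centres over three years, or 9589/3000 = 3.2 years with 30 centres.
4. Express the threshold as one rate, since 2 per week (104 per year) and 100 per year differ.
5. Show any table of power by opening delay only as an illustration, with its assumptions stated.

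The cost is a few restated figures and a slightly less favourable feasibility bar; no extra pilot patients are needed. A Day 90 measure matures later than a Day 30 one. Six months in, it covers only participants recruited in about the first three months, so it may be better read at the steering committee meeting planned after eight months of recruitment.
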